## II. SPECIFIC AIMS

The specific aims of this experiment are as follows:

[figure not shown]
- **Aim 1: To evaluate the efficacy of tDCS and mirror therapy (MT) as rehabilitative tools for the management of chronic PLP patients.**

We will explore the aim 1 in a randomized factorial controlled trial in which patients will be assigned to one of four groups: active tDCS and active MT; sham tDCS and active MT; active tDCS and sham MT (which consists of using a covered mirror for the therapy); and both sham tDCS and sham MT (covered mirror).

The primary end point will be severity of pain measured by changes in PLP as indexed by a Visual Analog Scale (VAS). The study will require a total of 13 weeks to be completed. The first week, each patient will give daily reports of their pain using a VAS, accounting for their PLP experience in the past 24hs. This initial baseline week will be followed by 4 weeks of treatment (tDCS and/or MT) and a final 8-week follow-up period without any treatment to examine long-lasting effects of each therapy. *Our hypothesis is that the combined intervention (tDCS and MT) will result in a greater pain reduction as compared with any therapy alone and no therapy.*

- **Aim 2: To examine the mechanisms underlying PLP using two neurophysiological techniques.**

For each of the four groups described in aim 1, we will determine the neural correlates of the effect. We will use single-pulse and paired-pulse transcranial magnetic stimulation (TMS) to assess cortical mapping and cortical excitability changes associated with cortical reorganization. We will also use functional magnetic resonance imaging (fMRI) to assess brain changes, including the quantification of maladaptive cortical reorganization. Using fMRI, we will determine the changes in Blood-Oxygen-Level dependent activation between the sensory-motor cortex of the affected and unaffected side after the treatment. We will compare these neurophysiological parameters before and after treatment in each of the four groups. *Our hypothesis is that the combined group (tDCS and mirror therapy) will have a greater activation than any therapy alone and also than the no therapy group (sham tDCS and covered mirror). This effect will also be correlated with pain reduction.*

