### *Screening Procedures:*

At Screening the PI and/or a co-investigator will conduct, once more a review of inclusion/exclusion criteria to determine the subject's eligibility for enrollment. Study procedures will be reviewed with the subject, and documentation of informed consent will be obtained.

At Screening the following procedures will be completed:

- Discuss study-specific procedures with the subject.

- Review inclusion and exclusion criteria.
- Obtain a signed and dated consent form.
- Conduct a Demographics Survey, Brief Medical History and Beck depression inventory.
- fMRI screening questionnaire\*.
- Urine pregnancy exam (if applicable).

\* If the subject is not eligible for an fMRI at the time of the study we will not perform this assessment as fMRI is not required for study eligibility and it is only used as a secondary outcome.

Randomization:

Once eligibility and consent have been approved and completed, randomization will occur using the randomized list generated by an automatic web-base randomization program ([www.randomization.com](http://www.randomization.com)). Subjects will be randomly assigned to one of the four groups in a 1:1:1:1 allocation ratio. We will use stratified randomization methods with random block sizes of blocks of 4 and 8. Patients will be stratified based on their baseline pain levels (two strata: less or equal of average 6 in VAS or more than 6 in VAS) and by study center (IMREA or SRH-Neuromodulation Lab). Randomization order will be kept in sealed envelopes; therefore subjects will get their assignment according to the order of entrance in the study (for instance, subject 1 will be assigned the first envelope that will contain his/her assignment according to this block randomization list).

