#### *For aim 1:*

[figure not shown]
The primary outcome is PLP indexed by VAS. PLP will be analyzed using intensity of pain over time. To analyze these data, we will initially build a mixed ANOVA model in which the dependent variable will be the outcome of PLP (such as VAS) and the independent variables will be group (active tDCS-MT; sham tDCS-MT; active tDCS and covered MT; sham tDCS- covered MT), time (baseline and after treatment and follow-up) and the interaction group\*time. In addition we will add the random variable ID to account for within subject’s variability and the repeated measures on time. We will initially perform this full model and, subsequently, post-hoc comparisons with corrections for multiple comparisons will be carried out initially to test our main hypotheses. Furthermore we will test the correlation in improvement between outcomes using Pearson’s correlation tests. P-values for secondary and exploratory outcomes will be determined without corrections for multiple comparisons. Finally we will apply a path analysis [60, 61] to the primary outcome data to determine if pain reduction associated with the combined intervention (tDCS and MT) is due to direct effects versus indirect effects through improvement in secondary outcomes. We propose that a direct effect of tDCS and MT on pain can be assumed if the treatment effect cannot be explained by changes in psychological or functional outcomes. Statistical models for pain will be developed using covariates that include site center, baseline

[figure not shown]
pain, psychological changes, functional changes, and the covariate treatment (main effect of treatment). To complete the path analysis separate regression models will be run to model the effects' of treatment on each outcome alone including all the secondary outcomes. Analyses of the secondary outcomes will be conducted in an exploratory manner (no correction for multiple comparisons). For the intention-to-treat analysis, we will use a conservative method and assume that participants will not improve from the last measured point. But we will also perform a sensitive analysis for the missing data using other methods such as completers only.

*For aim 2:*

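### The plan infers a direct effect on pain from failure to explain it away, and its Pearson correlations of improvement carry no treatment-arm term; mechanism claims are affected, the primary comparison is not (minor).

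*Combined protocol and SAP*

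**What the plan says.** The statistical section for Aim 1 (VI. Biostatistical Analysis) starts from a mixed ANOVA with group, time and their interaction. Two further analyses follow.

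- **Correlations.** The plan states that "we will test the correlation in improvement between outcomes using" Pearson's test. It does not say whether the arms are pooled, analysed separately or adjusted for. Aim 2 (II. Specific Aims) predicts greater activation with the combined treatment and adds: "This effect will also be correlated with pain reduction". The fMRI description in section V repeats this. Neither place names an arm term.
- **Path analysis.** This is applied "to the primary outcome data to determine if pain reduction associated with the combined intervention" is direct or runs through secondary outcomes. The rule, which concerns psychological and functional mediators, is: "We propose that a direct effect of tDCS and MT on pain can be assumed if the treatment effect cannot be explained by changes". The pain models include site, baseline pain, psychological change, functional change and treatment. The section gives no criterion for when an effect counts as explained, and no interval or assumptions for the direct and indirect parts.

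The section also says: "Analyses of the secondary outcomes will be conducted in an exploratory manner". It does not expressly give the path analysis that label.

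**The concern.** The path rule draws a positive conclusion from a failure to explain. A treatment effect can survive adjustment for a mediator because it bypasses the mediator, but also because the mediator is measured with error or another pathway was not measured. The rule treats all of these as a direct effect.

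The correlation problem arises from the trial's own hypotheses. The combined arm is expected to have both the largest pain reduction and the largest activation. If so, a correlation across all patients appears even when, within every arm, a patient's neural change says nothing about that patient's pain change. Such a correlation is real, but it partly restates the arm difference and cannot by itself support a patient-level mechanism.

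At stake are the statements on neural correlates of pain relief and on direct versus indirect effects. The risk is a mechanism claim stronger than the data allow.

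**Working it through.** **1. The plan's own figure.** No figure is given for the correlations or the path analysis. The only usable inputs are in the sample size paragraph: means 5.2 and 6.4, SDs 1.5 and 1.6, two-sided alpha 0.05, power 80%, 27 per group.

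- SD = √((1.5² + 1.6²)/2) = √2.405 = 1.551.
- n per group = 2 × (1.960 + 0.842)² × 2.405 / 1.2² = 26.2, so 27. This reproduces the plan.
- Standardised pain shift d = 1.2/1.551 = 0.774.

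**2. Path rule under full mediation.** Let treatment shift the mediator by a, and let pain depend only on the mediator with slope b. The total effect is ab and the true direct effect is 0. If the mediator's within-arm reliability is R, its regression slope shrinks to bR. The treatment coefficient is then ab − abR = ab(1 − R), so the false direct share is 1 − R whatever a and b are.

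| Reliability (assumed) | One mediator: 1 − R | Two parallel indicators: 1 − 2R/(1 + R) |
|---|---|---|
| 0.9 | 10% | 5% |
| 0.8 | 20% | 11% |
| 0.7 | 30% | 18% |

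Simulation with 27 per arm agrees. With a total effect of 0.775 and R = 0.8 the mean leftover was 0.151, against 0.155 from the formula.

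**3. Pooled correlation with no within-arm link.** Take unit SD within arms, 27 per arm, pain shift d = 0.774 and marker shift m (assumed). Let v be the variance of the arm pattern across four equal arms.

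- r = v·d·m / √((1 + v·d²)(1 + v·m²))
- z = atanh(r) × √(108 − 3)
- P(p<0.05) ≈ Φ(z − 1.96) + Φ(−z − 1.96)

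Example: combined arm only, m = d. Then v = 3/16 and v·d² = 0.1875 × 0.599 = 0.112. So r = 0.112/1.112 = 0.101, z = 1.04 and P = 0.179 + 0.001 = 0.18.

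| Which arms shift | v | m = d/2: r, P | m = d: r, P |
|---|---|---|---|
| Additive (each single therapy half, combined full) | 1/8 | 0.036, 6.6% | 0.070, 11.0% |
| Combined arm only | 3/16 | 0.053, 8.4% | 0.101, 18.0% |
| Both active tDCS arms | 1/4 | 0.069, 10.8% | 0.130, 26.9% |

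Simulations of 20,000 runs with equal shifts gave 11%, 18% and 27–28%. The arm-adjusted correlation rejected in about 5% throughout. The fMRI set may be smaller than 27 per arm, because "fMRI is not required for study eligibility and it is only used as a secondary outcome"; the documents give no expected number.

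**The case against.** The strongest reply is that much of the adjustment is already planned and the rest is exploratory. Part of this stands.

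- **Existing adjustment.** A reader might infer that the mechanism analyses ignore treatment arm altogether. They do not: the path regressions contain treatment, site and baseline pain. The gap is limited to the Pearson tests, chiefly the TMS or fMRI link with pain.
- **Separate tests in each arm.** A reader might infer four small within-arm tests from "For each of the four groups described in aim 1, we will determine the neural correlates of the effect". In context that sentence introduces the TMS and fMRI measurements, and the sentence on correlation with pain does not mention groups. The documents do not support building on that reading.
- **Type I error.** The plan promises only a correlation between improvements and states no within-arm target. The pooled rates above are therefore not false-positive rates for the stated test. They count against the analysis only when the result is read as a patient-level link.
- **Frequency of a wrong verdict.** A reader might infer that the path rule would mislead in a large, known fraction of trials. That cannot be shown. The plan sets no threshold for explained, and one may lie in the method references it cites. Full mediation of 0.774 SD with a mediator–pain correlation of 0.6 to 0.8 also needs a mediator shift of 0.774/0.8 = 0.97 to 0.774/0.6 = 1.29 SD, more than pain itself moves. The leftover share of 1 − R does not depend on that shift.
- **Direction of bias.** If mood follows pain, adjustment understates the direct effect and the rule becomes conservative. The bias is not all one way.
- **Exploratory status.** The path analysis uses the primary outcome data and is not expressly labelled exploratory. Such a label would not make the inference sound in any case.

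**Conclusion.** The point holds at minor severity. The direct-effect rule is an invalid inference, not merely a missing detail: under full mediation about 10–30% of the effect would look direct at assumed reliabilities of 0.9–0.7 with one mediator, and roughly 5–18% with two parallel indicators. The missing arm term in the Pearson tests is a narrower gap. If the arms are pooled, a correlation with no within-arm basis reaches p<0.05 in about 6–11% of trials when the marker shifts half as much as pain, and 11–28% when it shifts equally, against 5% when adjusted.

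Reliabilities, marker shifts and arm patterns are assumptions; only d = 0.774 and 27 per arm come from the plan. A reader might infer that the efficacy result is in doubt. It is not: the group-by-time model and the between-group activation comparison use neither analysis.

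**What to change.** (a) Specify the correlations of improvement, including the TMS and fMRI links with pain, as partial correlations, or as regressions of pain change on marker change, adjusted for arm, site and baseline values. Show unadjusted or by-group coefficients as description only.

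(b) Replace the sentence that lets a direct effect be assumed with wording that refers to the part of the effect not explained by the measured mediators. Report direct and indirect estimates with confidence intervals, as associations. State that they assume no unmeasured mediator–outcome confounding, no reverse causation and no mediator measurement error.

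**Cost.** SAP wording only; no new data. Adjusted correlations will usually be smaller. At a within-arm r of 0.3 and 27 per arm, simulated power (adjusted against pooled) is:

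- 88% against 89% when treatment shifts neither outcome;
- 88% against about 84% when it shifts pain only;
- 88% against 96–99% when it shifts both equally, because the pooled test then also counts the arm difference.

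If only 13 per arm had fMRI (assumed), adjusted power would be about 56–57%. A sensitivity analysis for mediator reliability, or the use of Visit 13 changes as mediators of later pain, is optional and not part of the correction.

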**Visit 2**

Baseline Visit – (Approximate Time: 2 hours)

*This visit might be completed on the same day as the screening visit if time allows and the subject agrees.*

Baseline assessments:

- Visual Analogue Scale (VAS) for Pain
- Visual Analogue Scale (VAS) for Stump pain
- Visual Analog Scale (VAS) for Phantom Limb Sensation
- Visual Analog Scale (VAS) for Phantom Limb Telescoping
- Adapted Groningen Questionnaire After Arm Amputation
- Pain and Medication use diary\*
- Beck Anxiety Inventory
- Mini Mental State examination (MMSE)
- Stroop Test
- Health Survey SF-36
- Single and paired pulse TMS
- Side Effects Questionnaire for TMS

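### The path model for direct and indirect effects lists mediator changes and baseline pain but no baseline mediator values, so its split may be biased in a direction the documents do not settle

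*Combined protocol and SAP*

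**What the plan says.** Section VI, Statistical Analysis, For aim 1, puts the path analysis after the mixed model and its post-hoc tests: "Finally we will apply a path analysis [60, 61] to the primary outcome data to determine if pain reduction" under the combined intervention is direct or indirect. The covariate list reads "Statistical models for pain will be developed using covariates that include site center, baseline" and continues "pain, psychological changes, functional changes, and the covariate treatment (main effect of treatment"). The mediators therefore appear only as changes.

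The decision rule is that a direct effect "can be assumed if the treatment effect cannot be explained by changes in psychological or functional outcomes". For the treatment-to-mediator paths, "separate regression models will be run to model the effects' of treatment on each outcome alone including all the secondary outcomes"; no covariates are named for these.

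Baseline mediator values will exist. Screening Procedures include "Conduct a Demographics Survey, Brief Medical History and Beck depression inventory", and the Visit 2 baseline list includes "Beck Anxiety Inventory" and "Health Survey SF-36". The plan does not say which score counts as functional; the SF-36 is assumed here.

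**The concern.** A change score is the post value minus the baseline value. It is usually negatively correlated with the baseline, because high scorers tend to fall and low scorers to rise. If baseline mood also carries information about later pain beyond what its change and baseline pain supply, leaving it out distorts the coefficient on the change. Whatever the mediator coefficient loses, the treatment coefficient gains, and the reverse.

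What is at stake is the mechanistic conclusion. The rule treats failure of the changes to explain the effect as grounds for assuming a direct effect, so attenuation of the mediator coefficient would push towards that conclusion for reasons unrelated to mechanism. This can happen with perfectly measured and correctly timed mediators.

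**Working it through.** The documents give no figure for the mediated share, so there is none to reproduce. All inputs in steps 2 to 5 are assumptions.

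**1. Algebra.** Let T be treatment, M0 the baseline mediator, ΔM its change, Y0 baseline pain and a the effect of T on the mediator. Write post-treatment pain as

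Y1 = c′T + bΔM + hM0 + gY0 + error.

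Omitting M0 turns b into b + hk and c′ into c′ − hka, where k is the slope of M0 on ΔM given T and Y0. The total, c′ + ab, is unchanged; only the split moves. With equal mediator variance before and after, stability ρ, and correlation q between M0 and Y0,

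k = −(1 − q²) / [(1 − ρ)(1 − q²) + 1 + ρ],

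which is negative. The direction of bias therefore depends on h: towards direct if h has the sign of b, none if h = 0, towards indirect if h has the opposite sign.

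**2. Pain follows the mediator's current level.** Let pain at each time be β times the current mediator plus a residual, with residual correlation r over time and standardised variables. Then b = β, h = β(1 − r), q = β. With ρ = 0.6 and β = 0.4,

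k = −0.84 / (0.4 × 0.84 + 1.6) = −0.84 / 1.936 = −0.434.

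The fraction of the mediated effect moved into the direct term is (1 − r) × 0.434. With full mediation this is the share of the total effect reported as direct.

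| r | Slope retained | Reported as direct |
|---|---|---|
| 0.3 | 0.70 | 30% |
| 0.5 | 0.78 | 22% |
| 0.7 | 0.87 | 13% |

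Simulations of this set-up with 400,000 or more subjects gave 29% to 31%, 21% to 22% and 13% to 14%. Over ρ = 0.4 to 0.8 and β = 0.3 to 0.5, k runs from −0.91/1.946 = −0.468 to −0.75/1.95 = −0.385, so the slope retained is 0.67 to 0.88 for r = 0.3 to 0.7. With M0 added, the simulations recovered 99% to 101% of the slope.

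**3. Other structures.** Take b = 0.8, a = −0.5, c′ = −0.8. The indirect effect is −0.4 of a total of −1.2, a true mediated share of 33.3%. With q = 0.4 and ρ = 0.5, k = −0.84/1.92 = −0.4375, and the planned model reports 0.5 × (0.8 − 0.4375h)/1.2.

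| h | Meaning | Planned model | Simulated | Simulated, M0 added |
|---|---|---|---|---|
| 0.8 | current level | 18.8% | 18.8% | 33.2% |
| 0.4 | intermediate | 26.0% | 26.1% | 33.3% |
| 0 | change only | 33.3% | 33.5% | 33.5% |
| −0.3 | opposite sign | 38.8% | 38.8% | 33.3% |

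A negative h can arise, for example, if pain's slope on mood is β0 before and β1 after treatment: then h = β1 − rβ0, which is negative when residual pain is persistent and the link weakens.

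**4. Confounding after baseline.** A shared cause of post-baseline mediator and pain was added to step 3, with stability 0.3 to 0.9. Against a true 33%, the planned model gave 25% to 57% and the model with M0 gave 42% to 53%. The planned model was closer to the truth in 11 of these 16 scenarios, because attenuation offset the confounding. The model with M0 was closer in the four with negative h, and one was a near tie. With measurement error in the mediator instead (SD 0.5, stability 0.6), the planned model gave 11% (current level) and 20% (change only); with M0 they were 25% and 21%.

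**5. Size against sampling error.** In the middle row of step 2, with an assumed 0.5 SD treatment effect on mood, the spurious direct effect is 0.5 × 0.4 × 0.217 = 0.043 SD. The plan's evaluable sample is 4 × 27 = 108. The residual SD of pain is √(0.84 × 0.75) = 0.794, so the standard error is at least 2 × 0.794/√108 = 0.15 (simulated: about 0.16). For two arms of 27 it is at least 2 × 0.794/√54 = 0.22 (simulated: about 0.23). The bias is thus 0.043/0.23 = 0.19 to 0.043/0.16 = 0.27 of a standard error. At r = 0.3 with 108 subjects, it is 0.061 against at least 0.17, rather more than a third.

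**The case against.** A reader might infer that the plan necessarily understates mediation and overstates the direct effect. The documents do not support that. They nowhere say whether pain follows the mediator's level or its change, and the plan's own wording concerns changes. Step 3 shows understatement, no bias and overstatement, depending on a coefficient nobody has stated.

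A reader might also infer that the plan has decided against baseline mediators. The list is introduced as covariates that the models will include, so it is open. The accurate statement is that these values are not listed.

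Nor are the treatment-to-mediator regressions biased for lack of a baseline. Treatment is randomised, so that path is protected; a baseline value there buys precision and consistency with the pain model.

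The strongest objection is that mediators are not randomised, and that mood and pain are self-reported at the same visits. With a shared cause, adding M0 can leave the estimate further from the truth than the planned model (step 4). That stands as a limit on the remedy. It is not a reason to omit a measured pre-treatment variable: the planned model comes closer there only because two errors happen to offset.

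Finally, the path analysis comes last, runs through secondary outcomes that the plan calls exploratory, and carries a bias well below one standard error in the scenarios of step 5. This limits the weight of the point.

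**Conclusion.** The point holds as a gap in specification. The pain model lists baseline pain and mediator changes but no baseline mediator values, and a stated inference about direct effects rests on it. The split is unbiased only if baseline mediator level has no effect on post-treatment pain given its change and baseline pain, a restriction the plan neither states nor justifies.

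If pain follows the current level, about 13% to 30% of the mediated effect is reported as direct (stability 0.6, slope 0.4, residual pain correlation 0.7 to 0.3). It is that share of the total effect only under full mediation. Other structures give no bias, or bias towards indirect. Without confounding or measurement error, the model with the baseline mediator recovered the truth in every structure tried, so the sign of h need not be known for the change to help.

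The primary group-by-time analysis, sample size and error rate are unaffected. At about 108 subjects the bias alone would rarely reverse a conclusion.

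**What to change.** In Section VI, For aim 1:

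- Name the mediators, and add each one's baseline value (depression, anxiety, and the score used as functional) to the pain model beside its change. This is equivalent to entering the baseline and post values.
- Put the same baseline value in that mediator's regression on treatment, for precision and consistency.
- State that this does not remove confounding of mediator and pain after baseline. Prespecify a sensitivity analysis, for example over a range of assumed correlations between the mediator and pain residuals, reporting where the conclusion changes.
- Replace the rule for assuming a direct effect with a report of the direct and indirect estimates and their confidence intervals, interpreted subject to that sensitivity analysis.

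The cost is a few sentences, one degree of freedom per mediator and a modest extra analysis. No new data are needed.
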